11.2 DEFINITION OF SOURCE DATA

Source data includes any hospital records and original (electronic or paper) questionnaires completed by any healthcare professionals or patients. It also includes PRO data collected at scheduled visits.

11.3 DATA COLLECTED

11.3.1 Patient Data

Patients will complete all PRO questionnaires in paper format. Physicians will handle the questionnaires to the patients to be completed. For baseline visit, patients will be asked to complete the questionnaires at the physicians' office/ waiting room, and give them back to the study nurse or physician.

During visit 1 the study nurse or physician will give the questionnaires for visit 3 to the patients to be completed at home within one week before visit 3. The same will be done at visits 3, 4, and 5. If visits 2 or 5 are not part of the site's routine clinical practice the patient will be given their questionnaires for their next planned study visit (visits 3 and 6).

If a designated caregiver is available to assist the patient, they may physically complete the questionnaire for the patient. A nurse or other health care professional may assist with instructing the patient on how to complete a questionnaire, in case they prefer to do it in the health care centre.

The completed questionnaires will be sent to the data management company to be entered into the study database.

11.3.2 Patient/Subject Tracking Logs

All consecutive patients who have started on Aubagio® in the past 4 weeks will be approached to enter the study. The patient's visit sequence will be documented in a patient tracking log for all enrolled and non-enrolled patients, with the reason for non-inclusion (not eligible or no consent). Data collected for patients who end up not enrolling are fully anonymous (gender, age).

The patient identification log for enrolled patients shall be kept by the Investigator to comply with the data privacy requirement. This log is not part of the eCRF and will not be entered into the clinical database.

11.4 PROCEDURE AND CONSEQUENCE FOR PATIENT WITHDRAWAL FROM STUDY

The participating Investigator should make every effort to re-contact the patient to determine his/her health status, including at least his/her vital status.

12 MANAGEMENT OF DATA

12.1 DATA COLLECTION, VALIDATION AND DATA QUALITY CONTROL

An eCRF will be provided by the Sponsor or a designated representative to record all clinical data.

Access to, and user roles in, the Electronic Data Capture (EDC) system and the corresponding domains will be managed and granted by the Sponsor or a designated representative. The confidentiality of all data collected using this EDC system is fully secured.

The computerized handling of the data by the Sponsor or a designated representative may generate additional requests, to which the participating Investigator is obliged to respond by confirming or modifying the data questioned (eQuery process).

Data collection and validation procedures will be detailed in appropriate operational documents (e.g., data validation plan) provided by the Sponsor or a designated representative and approved by the Sponsor.

12.2 MONITORING AND DATA QUALITY CONTROL AT SITE LEVEL

The EDC System will include integrated central data monitoring, quality check programs, and data management procedures (electronic query management) in order to supervise data recordings and to ensure completeness and high quality of all collected clinical data.

Data quality control (site monitoring) will be performed at site level by qualified monitors, according to the Study Manual.

Upon request, written informed consent forms, completed questionnaires, notes and copies of laboratory and medical records should be available at all times for monitoring or audits by the Sponsor's clinical professionals, and for inspections by authorities.

The Sponsor's representative, auditor, or inspector may review written informed consents and recordings in the eCRFs as deemed necessary and appropriate, and the accuracy of the data will be verified by reviewing the above referenced documents.

13 MANAGEMENT AND REPORTING OF ADVERSE EVENTS/ADVERSE REACTIONS

All AEs, regardless of seriousness or relationship to Aubagio®, spanning from the first Aubagio intake after the signature of the informed consent form until the end of the study as defined by the protocol for each patient are to be collected by the Investigator and reported to the Sponsor within an expedited time frame.

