Safety (AEs/SAEs/AESIs) since first dose of Aubagio will be retrospectively collected upon signature of the Informed Consent Form.

Visit 2 (Month 3) – only performed if part of routine clinical care.

- Prior and concomitant medications
- Number of relapses since last visit
- Treatment adherence number of missed doses since last visit
- Number of scheduled and unscheduled HCP encounters since last visit
- Number of emergency visits since last visit
- Safety information (AEs/AESIs/SAEs).

V3, V4, V5* V6/EOS

- Prior and concomitant medications
- Number of relapses since last visit
- MSIS-29
- MFIS-5
- HADS
- SDMT

- MSISO-19
- TSQM v1.4
- PDDS
- Treatment adherence Number of missed doses since last visit
- Number of scheduled and unscheduled HCP encounters since last visit
- Number of emergency visits since last visit
- HRPQ-MS (months 12 and 24/EOS only)
- Safety information (AEs/AESIs/SAEs)
- * Visit 5 only performed if part of routine clinical practice

Safety

- AEs/AESIs/SAEs since first dose of Aubagio® will be retrospectively collected upon signing Informed Consent Form.
- AEs/AESIs/SAEs will be recorded at each visit according to standard clinical practice
- Up to 3 Monthly telephone calls may be performed as and when needed in order to follow up on potential AEs/AESIs/SAEs.
- Patients will be followed with laboratory monitoring in a regular healthcare setting in line with local approved label requirements and the RMP for Aubagio[®].

STATISTICAL METHODOLOGY

The following represents an overview of planned analyses. Further elaboration of statistical issues will be specified in the Statistical Analysis Plan (SAP).

Sample size determination

The sample size has been calculated in order to assess the primary objective, describe changes in MSIS-29 scores from baseline to month 24. Mean MSIS-29 score on baseline, 24 months and changes during the follow-up (baseline to 24 months) will be calculated with the 95% confidence interval (CI). Taking into account a standard deviation of 20 points in MSIS-29 (Glenn, 2016), a sample size of 100 allows to estimate the MSIS-29 scores with a precision (distance from the mean to the limits of the 95% CI) of about 4 points with a significance level of 0.05. The sample size of 100 patients has been also determined based on the average number of patients at each site within the recruitment period of 2 years.

Analysis populations

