2.2 STUDY FLOW CHART

				Core Study		
Visits (V)	V1	V2 (if part of clinical practice)	V3	V4	V5 (if part of clinical practice)	V6/EOS
Months	Baseline ^a	M3 ±1 month	M6 ±1 month	M12 ±1 month	M18 ±1 month	M24 ±1 month
Eligibility (according to SmPC)	Х					
Patient Information / Informed Consent	Х					
Demographics (gender, year of birth, smoking history ^b)	Х					
MS disease history (date of first symptoms, date of diagnosis, number of relapses in the past 2 years, time since last relapse, disability progression / current EDSS)	Х					
Previous DMTs (previous drugs), current drug, time since treatment) $^{\it c}$	Х					
Reason to start/change DMT	Х					
Prior and concomitant medications	Х	Х	Х	Х	Х	Х
Number of relapses since last visit		Х	Х	Х	Х	Х
MSIS-29	Χď		Xi	X ⁱ	Xi	X ⁱ
MFIS-5	χď		X ⁱ	X ⁱ	Xi	X ⁱ
HADS	χď		Xi	Xi	Xi	X ⁱ
SDMT	Χď		Х	Х	Х	Х
MSISQ-19	χď		Xi	X ⁱ	Xi	Xi
TSQM v1.4	Xc,d		X ⁱ	X ⁱ	Xi	X ⁱ
PDDS	X _q		X ⁱ	X ⁱ	Xi	X ⁱ
Treatment adherence to Aubagio (number of missed doses since last visit)		Х	Х	Х	Х	Х
Number of unscheduled and scheduled HCP encounters ^f	Х	Х	Х	Х	Х	Х
Number of emergency visits ^f	Х	Х	Х	Х	Х	Х
HRPQ-MS	X ^d			X ⁱ		Xi
AEs, AESIs, SAEs ^e	Х	Х	Х	Х	Х	Х

- a Baseline visit completed within 4 weeks of first dose of Aubagio[®].
- b Smoking history includes current/former smoker, average consumption, pack years exposure, and time since cessation of smoking (if applicable).
- *c* Patients with previous DMT.
- d Within 4 weeks of first dose of Aubagio[®].
- e AEs (including SAEs & AESIs) within 4 weeks after first dose of Aubagio® will be retrospectively collected upon signing of the informed consent and on an ongoing basis including scheduled visits (eg., patients should report all AEs, SAEs and AESIs during the study period).
- f For baseline this is over the past 12 months
- g Performed in accordance with the local approved SmPC and the Aubagio $^{\circledR}$ RMP
- h In addition to study visits there may be up to 3 monthly telephone calls in order to follow up on potential AEs/AESis/SAEs

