7.2 DURATION OF STUDY PARTICIPATION FOR EACH PATIENT

The duration of the study for each patient will be 2 years (24±1 months). There will be a maximum of 6 study visits for participating patients. Data collection will be at baseline (Visit 1) and at month 3* (Visit 2), month 6 (visit 3), month 12 (visit 4), month 18* (visit 5), and month 24/End of study (EOS).

The baseline visit should occur within 4 weeks of the first dose of Aubagio[®]. All other visits should occur within a time window of ±1 month.

Note that not all study sites will have a month 3 and / or month 18 office visit, according to local practice, but if a month 3 and/ or month 18 visit is performed, data will be collected). Additional visits may occur according to the local clinical practice.

Eligible patients who meet the inclusion and exclusion criteria and sign the informed consent will be enrolled into the study.

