7.3.1 Baseline Visit

The following patient characteristics will be recorded at the baseline visit (completed within 4 weeks of first dose of Aubagio®):

- Patient demographics (gender, year of birth, smoking history)
- MS disease history
 - Date of first symptoms: month and year
 - Date of diagnosis: month and year
 - Number of relapses in the 2 years prior to enrolment
 - Time since last relapse
 - Disability progression/Expanded Disability Status Scale (EDSS) score
- Previous/current treatment with DMTs, if applicable
 - Treatment start and stop dates
 - Reason for starting/changing treatment
- Prior and concomitant medications
- Medical/surgical history and co-morbidities
- PROs (collected within 4 weeks of first dose of Aubagio®):
 - Multiple Sclerosis Impact Scale (MSIS-29) questionnaire
 - Modified Fatique Impact Scale (MFIS-5) questionnaire
 - Hospital Anxiety and Depression (HADS) guestionnaire
 - Symbol Digit Modalities Test
 - Multiple Sclerosis Intimacy and Sexuality (MSISQ-19) Questionnaire
 - Treatment Satisfaction Questionnaire for Medication version 1.4 (TSQM v1.4) questionnaire
 - Patient Determined Disease Steps (PDDS) questionnaire
- Number of scheduled and unscheduled HCP encounters within the past 12 months
- Number of emergency visits in past 12 months
- Health Related Productivity Question-MS (HRPQ-MS) questionnaire
- AEs/SAEs/AESIs since first dose of Aubagio® will be retrospectively collected upon signature of Informed Consent Form

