8.2 INCLUSION CRITERIA

- I 01. Adult patients (≥18 years old) with RRMS according to a neurologist's diagnosis, where the physician together with the patient have decided to start treatment with Aubagio® according to the approved SmPC.
- I 02. Initiated Aubagio® treatment for the first time within 4 weeks of study entry
- 103. Patients who have signed written informed consent
- 104. Patients who are willing and able to complete the questionnaires for the full duration of the study

Note: (if a designated caregiver is available to assist the patient, they may physically complete the questionnaire for the patient)

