13.1.3 Obligations of the Investigator regarding safety reporting

Adverse Event collection

All AEs, regardless of relationship to Aubagio® spanning from the first dose of Aubagio® after signature of the informed consent until the end of the study as defined by the protocol for each patient, are to be recorded

Property of the Sanofi group - strictly confidential

Version number: Final 2.0

immediately (within 24 hours of awareness) for serious AE and AESI and within 30 days of awareness for non-serious AEs on the corresponding page(s) of the eCRF as explained below. Assessment of causality of the AE to the study drug should be recorded (i.e., related, not related) as well as information about assessment of intensity and outcome of the AEs.

Laboratory and vital signs abnormalities are to be recorded as AEs only if they are medically relevant: symptomatic, requiring corrective treatment, leading to treatment modification (delay, reduction, or discontinuation) and/or fulfilling a seriousness/adverse event of special interest criterion.

Adverse Event reporting to Sanofi

Serious Adverse Events and Adverse Events of Special Interest In the case of an SAE or AESI the Investigator must immediately:

• Enter the information related to the SAE or AESI in the appropriate screens of the eCRF and SEND (within 24 hours of awareness, preferably by email or fax) the signed and dated corresponding page(s) in the Case Report Form to the Sponsor:

E-mail: [contact]

International Toll Free [contact]

Back up Fax 1: [name] Back up Fax 2: [name]

ATTACH the photocopy of all examinations carried out and the dates on which these examinations were
performed. Care should be taken to ensure that the patient's identity is protected and the patient's
identifiers in the study are properly mentioned on any copy of source document provided to for
laboratory results, include the laboratory normal ranges;

All further documentation should be sent to the Sponsor within 24 hours of knowledge. In addition, any effort should be made to further document each SAE that is fatal or life threatening within the week (7 days) following initial notification.

A back-up plan is used (using paper forms) in case the eCRF system does not work.

Non-Serious Adverse Events

In the case of an AE that does not meet the criteria for serious, the Investigator must:

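### Sections 13 and 13.1.3 start adverse event collection at the first intake after consent, but the synopsis, flow chart and Section 7.3.1 start it at the first dose, leaving 0 to 28 days of early treatment under conflicting rules

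*Protocol*

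**What the plan says.** The protocol gives two start points for safety data.

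**First intake after consent.** Section 13 defines the events that the investigator must collect and report to the sponsor as those "spanning from the first Aubagio intake after the signature of the informed consent form until the end of the study". Section 13.1.3, which sets out the investigator's duties, uses the same start point for recording in the eCRF: "spanning from the first dose of Aubagio® after signature of the informed consent until the end of the study".

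**First dose, collected retrospectively.** The Visit 1 list in the synopsis reads "Safety (AEs/SAEs/AESIs) since first dose of Aubagio will be retrospectively collected upon signature of the Informed Consent Form", and the synopsis repeats the rule in its safety list. Footnote e to the flow chart in Section 2.2 says that events "within 4 weeks after first dose of Aubagio® will be retrospectively collected upon signing of the informed consent". Section 7.3.1 says "AEs/SAEs/AESIs since first dose of Aubagio® will be retrospectively collected upon signature of Informed Consent Form".

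Entry rules let patients be on treatment before they consent. Inclusion criterion 2 in Section 8.2 is "Initiated Aubagio® treatment for the first time within 4 weeks of study entry". Section 7.2 adds "The baseline visit should occur within 4 weeks of the first dose of Aubagio". Section 11.3.2 describes recruitment in the same way: "All consecutive patients who have started on Aubagio® in the past 4 weeks will be approached to enter the study".

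Section 14.3.2 reports the frequency and percentage of patients with AEs, SAEs and AESIs. Under Section 14.2, the population is all enrolled patients with at least one dose.

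**The concern.** The wording in Sections 13 and 13.1.3 does no harm where consent comes before treatment, because the first intake after consent is then the first intake of all. In this study the order is often reversed. Aubagio is taken once daily (Section 5.2), so for a patient already on treatment who takes it as prescribed, the first intake after consent is simply the next tablet. Everything between the true first dose and consent falls outside the period that Section 13 defines.

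The time at stake is the start of treatment. Section 13.2 wants immediate notification of events such as raised transaminases, severe skin or allergic reactions and marked rises in blood pressure. Under the Section 13 rule, such an event before consent need not be recorded; under Section 7.3.1 it must be. The denominator in Section 14.2 is defined by dosing, which fits collection from the first dose better than collection from consent.

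**Working it through.** The protocol states no figure to reproduce here. The check sets the passages side by side and measures the disputed period.

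**Step 1. The rule in each place**

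| Place | Start of the period | Activity governed |
|---|---|---|
| Section 13 | first intake after consent | collection and reporting |
| Section 13.1.3 | first dose after consent | recording in the eCRF |
| Synopsis, Visit 1 list and safety list | first dose | retrospective collection |
| Section 2.2, footnote e | first dose (events in the following 4 weeks) | retrospective collection |
| Section 7.3.1 | first dose | retrospective collection |

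The first rule appears twice, so it is not an isolated slip. No passage says that Section 13 covers only prospective reporting, or that the retrospective events are an addition to it.

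**Step 2. Who is affected**

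Let d be the days from first dose to consent.
- Consent at or before the first dose: d = 0, and the two rules give the same period.
- Already on treatment at consent: d > 0, and the rules differ by d days.
- Limit set by Sections 8.2 and 11.3.2: d = 4 × 7 = 28 days.

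The disputed period is therefore 0 to 28 days per patient. The protocol does not say how d is distributed.

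**Step 3. Share of time**

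Follow-up is 24 months (Section 7.2), or 2 × 365.25 = 730.5 days. Two denominators are reasonable:
- share of a 24-month period = d / 730.5
- share of total time on treatment, if the 24 months run from entry and the patient stays on Aubagio = d / (730.5 + d)

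| d (days) | d / 730.5 | d / (730.5 + d) |
|---|---|---|
| 0 | 0% | 0% |
| 7 | 1.0% | 0.9% |
| 14 | 1.9% | 1.9% |
| 28 | 3.8% | 3.7% |

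**Step 4. From time to events**

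This step cannot be taken. It needs an event rate for the first weeks on treatment, the share of affected patients with no later event, the distribution of d, and the rule each site follows. The protocol gives none of these. A share of time is not a share of events, and it could misstate the loss in either direction if events are not spread evenly over the two years.

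**The case against.** The strongest reply is that the protocol says where its collection schedule lies. Section 11 refers to Section 2.2 for the data and timing, and Section 11.1 asks for all data outlined for each visit. Footnote e in Section 2.2 requires retrospective collection, the synopsis and Section 7.3.1 agree, and nothing in Section 13 forbids it. A site that omitted these events would be departing from the Visit 1 schedule. There is also one eCRF, with validation procedures and central monitoring (Sections 12.1 and 12.2). This makes it likelier that the retrospective rule would prevail in practice. It does not settle the conflict. Section 13 speaks of collection as well as reporting, Section 13.1.3 sets the recording duty, and reading them as limited to prospective events is an inference that the text does not state.

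A second reply is that some patients may consent close to the first dose, since Section 8.4 recruits upon the decision to treat. That is fair, and it is why the range starts at 0. Section 11.3.2 shows that others will already be on treatment.

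A third reply is that the study has a single arm and is descriptive. Safety is an endpoint but not a stated objective, and the MSIS-29 result is untouched. All of this is correct. It limits the consequence to the safety tables and safety reporting.

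Three stronger readings are tempting. A reader might infer that the percentage of patients with any AE would shift by many points. That would need an early event rate that the protocol does not give, the early period to lie wholly before consent, no later event in the affected patients over the rest of follow-up, and all sites applying the narrower rule. A reader might also infer that sites will in fact differ. No passage shows this; it is a possibility that the wording leaves open. Finally, a reader might infer that recording deadlines would start before the site could know of the event. Section 13.1.3 already runs them from awareness: 24 hours for SAEs and AESIs, 30 days for non-serious AEs. What remains is narrower: those deadlines are attached to events in the post-consent period, so the text does not plainly extend them to earlier events found at Visit 1.

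**Conclusion.** The contradiction is real, and the protocol does not resolve it. Sections 13 and 13.1.3, followed as written, exclude events from the start of treatment that the synopsis, Section 2.2 and Section 7.3.1 require. The excluded time is 0 to 28 days per patient, at most about 3.7 to 3.8% of follow-up time. The maximum rests on the 4-week entry limit, and the percentages also assume a full 24 months of follow-up. The number of events lost is not known and cannot be derived from the protocol.

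The Section 14.3.2 percentages could mix two collection rules across the approximately 20 sites (Section 8.1), but only if sites follow different sections. The point needs no assumption about event rates: a safety-collection rule is wrong as written for patients the protocol expects to enrol, and a short amendment removes the conflict.

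**What to change.** Amend the opening sentence of Section 13 and the matching sentence of Section 13.1.3 so that collection and recording begin at the first dose of Aubagio, with events before consent recorded retrospectively at Visit 1 once consent is signed. This is the start point already given in the synopsis, Section 2.2 and Section 7.3.1, so those need no change.

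In Section 13.1.3, add that the existing 24-hour and 30-day deadlines, counted from awareness, also apply to pre-consent events learned of at Visit 1. No new deadline is needed.

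An eCRF flag for retrospectively collected events would allow separate tabulation, but it is optional.

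The cost is two amended sentences and one clarification, with no added visit, questionnaire or patient burden, because Section 7.3.1 already calls for these data. Section 18 requires a written amendment signed by the investigator and notes that a regulatory submission may be needed.

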13.1 SAFETY INSTRUCTIONS

All events will be managed and reported in compliance with all applicable regulations.

13.1.1 Definitions of Adverse Event (AE) and Serious Adverse Event (SAE)

An Adverse Event is any untoward medical occurrence in a patient or clinical investigation patient administered a pharmaceutical product and which does not necessarily have to have a causal relationship with a treatment.

A Serious Adverse Event is any untoward medical occurrence that at any dose:

- Results in death or;
- Is life-threatening or;
- Note: The term "life-threatening" in the definition of "serious" refers to an event in which the patient was
 at risk of death at the time of the event; it does not refer to an event which hypothetically might have
 caused death if it were more severe.
- Requires inpatient hospitalization or prolongation of existing hospitalization or;
- Results in persistent or significant disability/incapacity or;

- Is a congenital anomaly/birth defect;
- Is a medically important event:
 - Suspected transmission of infectious agent is any suspected transmission of an infectious agent via a medicinal product (e.g., product contamination)

Medical and scientific judgment should be exercised in deciding whether expedited reporting is appropriate in other situations, such as important medical events that may not be immediately life-threatening or result in death or hospitalization but may jeopardize the patient or may require intervention to prevent one of the other outcomes listed in the definition above.

Adverse Event of Special Interest (AESI) See section 13.3 for definition and list of AESIs

